## 1. EXECUTIVE SUMMARY

Early mobilization stands for the mobilization in the early course of critically ill patients after admission to the intensive care unit. The positive impact of early mobilization of critically ill patients on various patient outcomes has already been demonstrated. However, the implementation of early mobilization in clinical practice is challenging. Especially the high personnel effort constitutes a barrier.

The Munich-based SME Reactive Robotics (RR) is currently developing the world's first adaptive robotic assistance system VEMO®, which has CE approval for the planned indication and aims to be used in the medium term for mobilizing intensive care patients.

Within the MobiStaR project, the adaptation of procedures in an intensive care unit combined with the use of this robotic system will create the conditions to significantly increase the mobilization rate of critically ill intensive care patients, possibly thereby increasing the rehabilitation outcomes for these patients and developing a new standard of care for robot-assisted early mobilization. The robotic system will be used in anesthesiological intensive care units of the LMU hospital. The protocol of the preliminary study to identify relevant problems, barriers and facilitating factors in the use of mobilization robots in the clinical setting and to record the current status of early mobilization with consideration of the professional groups involved has already been submitted to the Ethics Committee (Clearing 20-883).

In project module four, the effects of robot-assisted early mobilization shall now be evaluated. This study contains three study arms, in which (1) the feasibility and practicability of robot-assisted early mobilization, (2) the behavior and experience of the mobilizing professionals and (3) the effect on patient outcomes will be evaluated.

The study is monocentric, prospective and interventional. It does not include invasive measures or blood sampling and has multiple data collection time points.

- (1) The feasibility study of robot-assisted early mobilization collects data on how many VEM therapies can be performed in how many patients and whether and which adverse events occur. This will be collected by project staff during the VEM therapies.
- (2) The behavior and experience of the mobilizing professionals will be evaluated using episodic interviews as well as standardized observations. Nurses with specialized training in anesthesia and intensive care, nurses and physiotherapists who have at least three years of professional experience in an intensive care unit as well as medical specialists who have completed their training as medical specialists or who have a leading position in an intensive care unit are included. In addition, the individuals have an employment contract at LMU Klinikum. Furthermore, the secondment to the anesthesiological intensive care units is an inclusion criterion.
- (3) The effects on patient outcomes, primarily duration of ventilation, muscle mass (sonographic examination) and physical activity (measured by established scores such as FSS-ICU and MRC classification), will be measured at different points in time and compared with a historical patient population. Secondary outcomes such as delirium incidence, hemodynamic parameters, respiratory parameters but also longitudinal parameters such as intensive care and hospital length of stay will be analyzed from routine data/patient records. Included are informed consenting patients who will undergo a planned surgical procedure that involves postoperative intensive treatment and an anticipated duration of ventilation of more than 48 hours. These patients will receive standardized early mobilization using the robotic system at either ten frequencies or for seven days. No invasive procedures such as blood sampling will be performed as part of the study. To evaluate the effect of robot-assisted VEM, the outcomes

will be compared with a historical comparison group. Approximately 30 patients shall be included. The results will be compared to a historical group (n=30) with conventional early mobilization.

The intervention is planned for a duration of five to six months starting in August 2021.

## 2. BACKGROUND AND RATIONALE

Many studies have shown that early mobilization of ICU (intensive care units) patients improves functional and cognitive health (1-7). The best possible rehabilitation is achieved (8) and the length of stay in the ICU and hospital is shortened (3). It has also been described that functional disorders can be prevented (9, 10). However, studies show mixed results regarding this (11-14).

The definition of early mobilization is not consistent across the literature (15). Many studies talk about early mobilization if it starts within 72 hours after admission to the ICU. Early mobilization of ventilated ICU patients is only feasible with an extraordinarily high level of personnel effort (16). Other factors such as sedation or unconsciousness of the patients or the period of treatment (e.g. at the weekend) also lead to the fact that only about 25% of the patients in the intensive care unit are mobilized (17). This has considerable consequences for the healing process of the patients as well as for the costs of treatment (9).

Currently, there are several devices on the market that allow automated robotic early mobilization therapy. Compared to manual early mobilization, robotic support has the advantage that mobilization in bed can reduce the risk of falls for patients. In addition, the physical strain for mobilizing professionals is reduced, as the robotic device takes over the verticalization and leg movement. Some models verticalize and mobilize patients. However, this requires the patient to be transferred from their bed to the training device and then back to the bed. Another product is a modern tilting intensive care bed, which allows passive movement of the legs.

The early mobilization robot used in our study design is able to verticalize the patients in their bed without transfer and generate a movement of the legs that measures and supports the patients' own movement. The device fulfills the requirements for mobilizing critically ill patients in an intensive care unit, maintaining hygiene standards and providing the best possible support for the patient's own movement.

The process of the overall project is based on the development model of complex interventions of the Medical Research Council (MRC) (18): In a cycle of piloting, evaluation, implementation and (further) development, the framework conditions for the use of the early mobilization device are created within the overall duration of the project (see Fig. 1).

[figure not shown]

Abb. 1: Medical Research Council: Key elements of the development and evaluation process (18)

As part of the preliminary study (Ethics Vote 20-883), support factors and barriers for integrating a robotic system into the clinical setting were evaluated using the following study components:

- Identification of relevant problems, barriers and facilitating factors in the use of mobilization robots in the clinical setting - The perspective of clinical experts and developers,
- Assessment of the Current Status of Early Mobilization in Intensive Care Units - The Perspective of the Professional Groups Involved and of Science

Based on the results of this study, robot-assisted early mobilization in intensive care units will now be investigated.

Evidence-based data on whether the use of robot-assisted early mobilization can improve patient outcomes, what the experience of users is like, and whether the implementation can be embedded organizationally and structurally in the daily routine of an intensive care unit are currently lacking.

The aim of the study is to investigate whether (1) robot-assisted early mobilization in intensive care units is feasible according to previously considered support factors/barriers, (2) which effect the integration of the device and the treatment has on the patient's outcomes, and (3) how the behavior and experience of the mobilizing professionals as well as the medical and nursing processes change. The three overall objectives will be considered in more detail under point five.

### 2.1.1. STATUS QUO OF EARLY MOBILIZATION IN GERMANY

In Germany, 2.1 million patients receive intensive care treatment every year. About 18% of them need artificial respiration temporarily (19). 20 - 30% of those affected are considered seriously ill patients who require artificial respiration over a longer period of time. About 20% of all patients in intensive care are considered to be critically ill, and the tendency is increasing.

Regular mobilization, meaning all forms and processes of mobilization aiming at the rehabilitation of intensive care patients, leads to a multitude of important positive healing processes and consequently to an overall faster recovery (20) (see Figure 2).

[figure not shown]

Figure 2: Comparison of rehabilitation duration with standard treatment and with early mobilization as therapy (21, 5, 22, 3, 23-27).

Regular mobilization, especially through assisted walking movements, reduces the risk of decubitus ulcers, maintains mobility and cardiac function, as well as facilitating bowel movements. In intensive

care units, these mobilizing measures are already part of the therapy program of less heavily affected patients (9, 28).

Clinical studies show that critically ill ICU patients who receive very early mobilization (VEM), i.e., mobilization performed within 72 hours of ICU admission, achieve the best possible rehabilitation (10). However, optimal VEM therapy requires daily mobilization of patients for at least 20 minutes, combining the verticalization of patients and the movement of their legs, according to a normal gait pattern.

Due to the critical physical condition of intensive care patients, VEM therapy can therefore only be carried out with an extraordinarily high level of personnel effort. Often, critically ill patients cannot stand on their own feet due to their severe limitations and have to be "exercised" on a therapy device. The transfer of intensive care patients from bed to a separate therapy device is time-consuming and not without risk for patients and is therefore not often performed in clinical practice. Active mobilization should be performed by at least two qualified staff members, as described in the current S2 guideline (S2e guideline: "Positioning therapy and early mobilization for prophylaxis or therapy of pulmonary dysfunctions" (29)).

For these and many other reasons, such as sedation/paralysis of the patients concerned (46%), unconsciousness (4%), staff shortage (17%), weekend (8%), etc. (30), only a quarter of the eligible patients are currently early mobilized (8, 17). This has considerable consequences for the healing process, the burden on relatives, and not least for the costs incurred by health insurances and the people insured.

#### 2.1.2. ROBOT-ASSISTED EARLY MOBILIZATION IN THE INTENSIVE CARE UNIT

The Munich-based SME Reactive Robotics (RR) is currently developing the world's first adaptive robotic assistance system for mobilizing intensive care patients. However, the path towards

- a nursing robot that can be used in a standardized manner for all eligible, critically ill patients,
- that sustains the quality of care,
- significantly improves the outcomes for patients and their chances of recovery,
- thereby relieving the personnel,
- that is economically attractive
- and is easily integrated into the processes of an intensive care unit

strongly depends on the environment, the processes and organizational procedures in which the robot is integrated.

---

Clinical intervention study – Project MobiStaR  
Study protocol Version 2.0 from 27.05.2021

The vision of integrating robot-assisted early mobilization into the daily routine of an intensive care unit is shown in Figure 3.

Figure 3: MobiStaR Vision: Verticalization and exercise of patients in their intensive care bed.

There is currently no adequate evidence for the benefit of the use of robotics in the early mobilization of ICU patients.

### 3. OBJECTIVES

The aim of this interventional study is to determine whether robot-assisted early mobilization of critically ill patients is feasible. In addition, it is intended to identify the effects of this form of VEM compared to conventional, manual VEM on the experience of the users and the outcomes of the patients.

To achieve this purpose of the study, the following research questions will be examined in the context of (1) organizational feasibility, (2) evaluation of effects on patient\* outcomes, and (3) evaluation of the mobilizing professionals' experience:

### 3.1. ORGANISATIONAL FEASIBILITY

- How many patients are suitable for robot-assisted VEM and how many are actually early mobilized with the robotic device? (Number of patients treated / number of suitable patients)
- In how many cases the conventional/robotic VEM could be performed completely? In how many cases did the robotic VEM have to be discontinued? (Number of completely performed VEMs in patients/ Number of treated patients/ Reasons for discontinuation)
- How was the early mobilization performed? (Duration of VEM and set-up times, frequency of VEM, intensity of VEM (number of steps per minute/ total number/ degree of verticalization).
- Could the planned procedure of the VEM be performed? (Number of aborted/ cancelled VEMs, number of VEMs carried out)
- Could the VEM become part of the daily routine of the ICU? And if not, what factors are influencing this? (Free text)
- Are the technical requirements for complete rehabilitative therapy using a robotic device available or have there been failures? (Number of failures)

Primary target criteria	Feasibility of early mobilization	
Suitability of patients for robotic VEM (number)
 
Frequency of treatment (completed number of treatments)
 
Duration of treatment and set-up times (in min)
 
Frequency of treatment
 
Intensity of treatment (comparison group using ICU Mobility Scale (31)
 
Number of failures of the technical system

	Adverse Events	
The following adverse events are defined as long as they occur during mobilization and up to 15 minutes afterwards:
 
New cardiocirculatory insufficiency (hypotension, hypertension, arrhythmia).
 
New respiratory insufficiency (drop in saturation, asynchrony with ventilator).
 
Accidental removal/dislocation of devices such as tubes, drains, catheters
 
Injury and fall
 
All serious adverse events will be analyzed and evaluated by the investigator to determine whether they occurred as a result of the study.

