The treatment team does not differ for the individual patients: it usually consists of nurses from the corresponding intensive care units, assigned physiotherapists and the corresponding ward physicians. For the duration of the study, an additional study team will be established, consisting of study physicians, study nurses and technical support from the manufacturer.

Robotic-assisted early mobilization should be performed within the first 72 hours postoperatively, if possible, and should be performed at least twice a day for 20 minutes until the seventh postoperative day or at least ten cycles of treatment during the intensive care unit stay.

Frequency of treatment, treatment duration and intensity are recorded. Treatment-associated events will be recorded.

In case of hemodynamic, respiratory or other instability during treatment, the therapy session can be discontinued at any time. The decision to discontinue mobilization rests solely with the treatment team. The study team can advise.

Fig. 10: Robot-assisted verticalization with VEMO©.

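### One primary feasibility criterion counts completed treatments without the sessions due, so full delivery in a short ICU stay cannot be told from partial delivery in a long one

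*Protocol*

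**What the plan says.** The primary criteria table in Protocol section 3.1 has six entries under feasibility of early mobilization, followed by a block for adverse events. The entry on delivery is "Frequency of treatment (completed number of treatments"). Frequency of treatment then appears a second time without a definition. The other entries include "Suitability of patients for robotic VEM (number"), "Duration of treatment and set-up times (in min") and "Number of failures of the technical system", plus treatment intensity. None of them sets sessions given against sessions due.

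The research questions above the table name some ratios and counts. One is "Number of patients treated / number of suitable patients". Another is "Number of completely performed VEMs in patients/ Number of treated patients/ Reasons for discontinuation", where the nearest denominator is patients, not sessions. A further question asks whether the planned procedure could be performed, and is to be answered by the numbers of aborted or cancelled VEMs and of VEMs carried out.

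The schedule is twice daily for 20 minutes. The course length is worded differently in section 1, section 5, the robot-assisted subsection of section 8, the opening of section 8.3, and the later robot-assisted subsection of 8.3. The last runs "until the seventh postoperative day or at least ten cycles of treatment during the intensive care unit stay". The executive summary gives ten or seven days without calling ten a minimum, and the opening of 8.3 allows two or more sessions a day.

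Section 8.1 lists what is recorded for each mobilization: date, postoperative day, running number, duration, and premature termination yes or no. Section 9 says that feasibility data are reported descriptively and then examined by regression.

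**The concern.** The question behind the criterion is whether the planned robot sessions can be given on a working ICU. A bare count answers a different question: how many sessions took place. Sessions can be given only while the patient is in the ICU, so the count moves with the start day and with ICU discharge or death as well as with the unit's ability to deliver. A low count may mean that the unit failed to deliver, or that the patient left early after receiving everything that was due.

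The link to stay also ties the measure to the patient outcomes. Duration of ventilation is a primary outcome and ICU treatment duration a secondary one (section 4.3), and section 10 names shorter ventilation as a possible benefit. If the robot shortened ICU stay, the count would fall with no change in delivery. The regression step in section 9 would carry the same dependence if the count is used there. Short stays are possible because patients are enrolled before surgery on expected, not observed, ventilation of more than 48 hours (section 7.2).

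**Working it through.** The protocol states no target or expected value for this count, so there is no figure to reproduce. The check is arithmetic on the protocol's own schedule.

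**Inputs from the protocol.** Two sessions a day (section 5 and the robot-assisted subsection of section 8); ten cycles or seven days; one wording ends at postoperative day 7.

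**Assumptions, for illustration.** Start day s, last ICU day L, two sessions on every day from s to L, full delivery. The documents give no distribution of ICU stay.

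**Formulas for attainable sessions, under three readings of the course end:**
- until postoperative day 7: 2 × (min(L, 7) − s + 1)
- stop at ten cycles: min(10, 2 × (L − s + 1))
- seven treatment days: 2 × (min(L, s + 6) − s + 1)

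| Last ICU day L | Start day 1: day 7 / ten / seven days | Start day 2: day 7 / ten / seven days |
|---|---|---|
| 3 | 6 / 6 / 6 | 4 / 4 / 4 |
| 4 | 8 / 8 / 8 | 6 / 6 / 6 |
| 5 | 10 / 10 / 10 | 8 / 8 / 8 |
| 6 | 12 / 10 / 12 | 10 / 10 / 10 |
| 7 | 14 / 10 / 14 | 12 / 10 / 12 |
| 10 | 14 / 10 / 14 | 12 / 10 / 14 |

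Every patient in the table received every session attainable from the first session on, yet the counts differ. For a day-1 start they run from 6 (2 × 3) to 14 (2 × 7). The increase stops once the ten-cycle or seven-day limit is reached, provided that limit ends the course. For long stays the three readings disagree, so the number of sessions due is itself not fixed.

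**Ranking of two patients:**
- A is treated on days 1 to 3 and then leaves the ICU: 6 due, 6 given, 6/6 = 100%.
- B is in the ICU for days 1 to 7: 14 due, 8 given, 8/14 = 57%.

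The raw count puts B (8) above A (6), while the proportion puts A above B. If the course is taken to stop at ten, B has 8/10 = 80% and the order by proportion is unchanged.

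**Where the denominator starts.** A patient treated on days 4 and 5 receives 2 × 2 = 4 sessions. Counted from the first session this is 4/4; counted from day 1 it is 4/10 = 40%. A proportion that starts at ICU admission would mix a late start with missed sessions, so the delay is better shown on its own.

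**Whether other items supply the denominator.** "Number of completely performed VEMs in patients/ Number of treated patients" divides by patients, so it varies with stay as the count does. The per-mobilization form is filled in when a mobilization takes place; it can show an early end but has no line for a session that was due and never began. The weekly counts in section 8.1 cover patients whose intervention was discontinued, not sessions missed.

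**The case against.** The strongest reply is that section 3.1 already asks for aborted or cancelled sessions alongside those carried out. That is a session-level view of delivery, and a session that falls after ICU discharge would not naturally be called cancelled. Reasons for discontinuation are also to be reported. This stands in part. The counts are not among the primary criteria, however, and the form in section 8.1 has no field that would produce a count of sessions never started.

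The second, undefined frequency entry could be read as a rate per day, which would depend less on stay. The protocol does not say so.

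It can also be said that denominators belong in a statistical analysis plan. For the calculation alone that is fair. But this protocol itself names the primary measure and lists the data, and reasons for sessions not given must be recorded at the time.

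A reader might infer more than the document supports:
- That this count is the sole primary feasibility criterion. It is one of six feasibility entries, beside an adverse-events block, and its unit (per patient or in total) is not stated.
- That a patient who recovers quickly is judged a feasibility failure. No threshold or decision rule exists, and reporting is descriptive.
- That fewer than ten sessions is a failure. The course is worded as ten cycles or seven days.

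**Conclusion.** The point holds as a weakness in one primary feasibility measure. As listed, the count cannot separate delivery from length of ICU stay: 6 of 6 sessions due (100%) records a lower value than 8 of 14 (57%). The effect is confined mainly to stays that end before the ten-cycle or seven-day limit, and it levels off after that if the limit ends treatment. The size rests on two sessions on every ICU day and on illustrative start and discharge days. How many patients would be affected cannot be derived, because no distribution of ICU stay is given.

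The consequence is a feasibility result that is hard to interpret. It is not a wrong decision, since no decision hangs on the count. A change is worthwhile because a proportion answers the protocol's own question about the planned procedure directly.

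**What to change.** 1. Reconcile the schedule wordings in sections 1, 5, 8 and 8.3, so that the number of sessions due is defined once. Which wording should stand is for the investigators.
2. Make the primary delivery measure, per patient, completed sessions divided by sessions due, counted from the first session until course end, ICU discharge or death, whichever comes first.
3. Show days from ICU admission to first session separately. Patients never treated have no proportion; they remain visible in the ratio of treated to suitable patients.
4. Count sessions withheld under the safety criteria (traffic-light system, section 8.3) as their own category, apart from sessions broken off and sessions missed for other reasons.
5. Add a log line for each due session not given, with its reason.
6. Keep the raw count as description, state its unit, and define or delete the second frequency entry.

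The cost is small: one definition and a short log entry per missed session. Mobilization dates and ICU treatment duration are already to be collected, and no extra examination of patients is needed.

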#### Patient-related data

Three-digit ID	postoperative day
Date	
Consecutive number of mobilizations	
Duration of mobilization	start - end (number of minutes)
Set-up time preparation	Number of minutes
Set-up time postprocessing	Number of minutes
Number of mobilizing professionals	Number
Intervention related data	
Degree of verticalization	Degree between 0 and 70
Number of minutes in the highest degree of verticalization	Number of minutes
Steps per minute	Number
Total steps	Number
Adverse event / premature termination	yes /no (If yes, type of event)
Feasibility assessment by mobilizing professional	7 point Likert scale
Assessment of the mobilizing professional's own physical stress	7 point Likert scale

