## 10. ETHICAL CONSIDERATION FROM THE PERSPECTIVE OF THE STUDY TEAM

The study itself is designed as a clinical intervention study with comparison to a historical patient population. Patient participation is voluntary. The value of early mobilization in critically ill patients has been proven, as has the safety of early mobilization. Harmful events occurred very rarely in comparable studies, and serious adverse events seen in association with the study did not occur (5, 16). The use of the VEMO© system has also been studied and found to be safe. Thus, participating patients have no a priori disadvantage. The VEMO© system has a CE certificate and is approved for the early mobilization of critically ill patients. It is categorized as a class 2a medical device and is in regular use in several German and international hospitals, such as the Berufsgenossenschaftliche Unfallklinik Murnau, the Schön Klinik Bad Aibling or the Universitätsmedizin Charité Berlin. The system is only used for the approved indication (early mobilization of critically ill patients). A hygiene concept for the application of the system was developed in cooperation with the hospital hygiene department. The surveys within the scope of organizational feasibility accompany the interventions and pose no risk to patients through the observational function.

Otherwise, the study team has no influence on the treatment of the patients.

The primary benefit in terms of effects on patient outcomes is to determine whether robot-assisted mobilization differs from conventional early mobilization in its ability to reduce ventilation time, muscle atrophy, and intensive care unit (ICU)-acquired weakness.

Individual patients could benefit from intensive robot-assisted early mobilization in terms of shorter ventilation, less muscle atrophy, and better physical functionality. A lasting negative impact in the patient group is not expected if treatment with a safe, non-invasive medical device and intensive physiotherapeutic exercise is performed. Serious adverse events associated with the medical device are not known. Possible adverse events such as short-lasting changes in blood pressure and heart rate, the accidental removal of drains or the development of skin lesions due to the mobilization cuffs could occur.

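### One 15-minute adverse-event window is applied to every event type, so the cuff skin lesions the protocol itself foresees can go uncounted, and whether device preparation is inside the window is left open.

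*Protocol*

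**What the plan says.** Protocol section 3.1 places adverse events among the primary target criteria of the feasibility arm and opens the list with "The following adverse events are defined as long as they occur during mobilization and up to 15 minutes afterwards". Four groups follow: new circulatory insufficiency, new respiratory insufficiency, "Accidental removal/dislocation of devices such as tubes, drains, catheters", and "Injury and fall". The time limit stands above all four. Serious adverse events are to be assessed by the investigator, with no separate period stated.

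Section 10 names the harms the study team considers possible. Besides brief changes in blood pressure and heart rate, it says that "the accidental removal of drains or the development of skin lesions due to the mobilization cuffs could occur".

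The per-session form in section 8.1 gives the duration of mobilization as "start - end (number of minutes". It has separate fields for "Set-up time preparation" and "Set-up time postprocessing", and a yes/no item for an adverse event or early termination.

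On collection, section 1 says project staff gather the feasibility data, adverse events included, during the therapies. Section 8 adds ward staff and ends the feasibility survey with the last robot-assisted session.

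**The concern.** A 15-minute limit is a sensible way to tie a fall in blood pressure or saturation to a session. A skin lesion under a cuff is different: it may develop, or be noticed, only after the cuff is off and the window has closed. These patients are expected to be ventilated for more than 48 hours (section 7.2), so many may be unable to report local pain promptly.

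Section 10 therefore foresees a device-specific harm that the primary definition in section 3.1 neither names nor gives a suitable period.

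The second gap concerns the start of the window. If preparation does not count as mobilization, a tube or drain dislodged while the device is being attached falls before it. Section 10 lists drain removal as a possible event.

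At stake is the completeness of a primary safety count in a small single-centre study whose results are meant to support a new standard of care (section 10). If such an event is not recorded, no later analysis can recover it.

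**Working it through.** The protocol states no adverse-event rate and no figure on this point, so there is nothing to reproduce. The check compares sections, with two small calculations.

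**1. Foreseen events against the definition**

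- Changes in blood pressure or heart rate: listed, and the window fits.
- Accidental drain removal: listed, and counted during the session and for 15 minutes afterwards. Preparation is unclear.
- Cuff skin lesions: not named. They can enter only as an injury, under the same limit.

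**2. Can another route catch a lesion found later?**

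- Weekly adverse-event counts and the per-session item (section 8.1): no time limit is stated, but both belong to the feasibility data, which are collected during therapies (section 1) and end with the last session (section 8).
- Documentation of complications (section 8, robot-assisted early mobilization) and recording of treatment-associated events (section 8.3): neither has a definition, period or method, nor a stated link to section 3.1.
- Decubitus grade 1 to 4 (section 4.3): a secondary outcome with no body site and no attribution to the device.
- Serious adverse events (section 3.1): do not reach non-serious lesions.

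No route assures a place in the primary count for a lesion found the day after the last session. For one found some hours after an earlier session, the answer depends on how the word occur is read.

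**3. Set-up time**

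Inputs: 20-minute session (section 8) and 15-minute tail (section 3.1). The length of set-up is not given, so equal preparation and postprocessing of *s* minutes is assumed. On the narrow reading, in which preparation is not mobilization:

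- handling time = *s* + 20 + *s*
- covered time = 20 + min(*s*, 15)
- uncovered share = 1 − covered / handling

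| *s* (min) | handling | covered | uncovered share |
|---|---|---|---|
| 5 | 30 | 25 | 17% |
| 10 | 40 | 30 | 25% |
| 15 | 50 | 35 | 30% |
| 20 | 60 | 35 | 42% |
| 30 | 80 | 35 | 56% |

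Up to *s* = 15 all the uncovered time is preparation, because postprocessing then lies within the tail. These are shares of handling time, not of events. If preparation counts as mobilization, the uncovered time is 0 for *s* up to 15.

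**4. Weight of one patient**

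Section 7.3 plans 30 to 35 treated patients. One patient whose only event is uncounted changes the observed proportion by 1/35 = 2.9% to 1/30 = 3.3%, in percentage points.

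**The case against.** The strongest reply has four parts.

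First, section 3.1 limits when an event occurs, not when it is seen. A skin injury caused by a cuff during a session and found that evening arguably occurred in the window, and injury is broad enough to include it. This stands as a possible reading. But the protocol does not say that late-found events are dated back to the session, and a lesion that evolves after the cuff is removed is not covered even then.

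Second, several recording routes carry no 15-minute limit, so the event may be documented somewhere. That is true, and it rules out saying that the trial will under-report. It does not settle whether such records enter the primary count.

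Third, the section 8.1 form treats preparation, postprocessing and adverse events as data of one mobilization. A reader might infer from the separate time fields that set-up is excluded. The protocol nowhere says so; the fields also serve the feasibility measure of set-up time. The defensible statement is that the boundary is undefined. Nor is line dislodgement a general gap, since it is listed and counted in the session and for 15 minutes after it.

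Fourth, a window around the session suits a measure of tolerability, and the protocol sets no safety hypothesis or threshold. This is a good reason to keep the limit for haemodynamic and respiratory events. It is weaker for skin injury.

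A reader might also compute the window as 35 minutes × 10 to 14 sessions = 350 to 490 minutes, or 3.5% to 4.9% of the 10,080 minutes in seven days, and infer that nearly all events are lost. That does not follow. It is the share of time covered, device-related events cluster around device use, and section 8.3 allows more than two sessions a day.

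**Conclusion.** The point holds in a limited form and should be corrected. The definition in section 3.1 does not name the cuff skin lesions foreseen in section 10 and gives them a window designed for acute reactions. The collection rules in sections 1 and 8 do not assure that a lesion developing or found later is counted. Separately, the start of the window is undefined with respect to preparation, so a dislodgement in that phase may be missed.

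The size in events is unknown. What can be said is that each affected patient is worth about 3 percentage points in this sample.

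The conclusion assumes that some cuff lesions become visible more than 15 minutes after a session; the protocol gives no data on this. It also assumes that the untimed recording routes are not already meant to feed the primary count. The documents do not support a claim that the trial would under-report harm or would wrongly conclude that the device is safe.

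**What to change.** Amend the adverse-event definition in section 3.1 and the form in section 8.1:

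- Name skin lesions at cuff and other device contact sites as adverse events. Count them whenever they are found at routine skin checks up to ICU discharge, with body site and a causality judgement.
- Start the event period at the beginning of preparation. For dislodgement, injury and falls, also state how postprocessing beyond 15 minutes is handled.
- Keep the 15-minute limit for haemodynamic and respiratory events.
- State that this definition governs the weekly and per-session counts in section 8.1 and the treatment-associated events in section 8.3, and extend skin-lesion collection beyond the last session accordingly.

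The cost is a few lines of text and one or two form fields. Because the decubitus grade is already collected, no new procedure should be needed, although the protocol does not state how often the skin is inspected. The drawback is that some lesions not caused by the device will be counted. Reporting all contact-site lesions alongside those judged device-related keeps this visible.
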